11.1. Participant Completion

After completing Visit 2, the subjects will have completed the study.

11.2. Participant Stopping Rules and Withdrawal Criteria

Participants may be prematurely terminated from the study for the following reasons:

1. The participant elects to withdraw consent from all future study activities, including follow-up.
2. The participant is “lost to follow-up” (i.e., no further follow-up is possible because attempts to reestablish contact with the participant have failed).
3. The participant dies.
4. The Investigator no longer believes participation is in the best interest of the participant.
5. A subject has more than one protocol-defined asthma exacerbation (defined as the development of an increase in symptoms of cough, chest tightness, or wheezing [independently of the symptoms anticipated to occur as a result of the aspirin challenge] requiring treatment with oral glucocorticoids. For those subjects maintained with a stable oral glucocorticoid dose, the definition will be an increase of ≥ 10 mg or a doubling of dose, whichever is less)
6. The subject experience gastrointestinal bleeding
7. The subject becomes pregnant

11.3. Participant Replacement

Additional participants will be recruited if a participants withdraw or are withdrawn if the termination occurs prior to receiving the first dose of the study medication (ifetroban or placebo).

11.4. Follow-up after Early Study Withdrawal

If a subject needs to discontinue any of the investigational drugs prior to the end of the study, we will ask him/her to come in for one final visit. During this visit we will ask them to return all unused medication, have one final blood draw (to make sure their complete blood count (CBC) is normal), and one final pregnancy test (if applicable). If the subject does not return for this final visit, a study investigator will attempt to speak to the subject by telephone, and if unreachable at their preferred contact number, a clear message regarding the importance of follow-up and study investigator contact information will be left. If a subject experiences an adverse event that results in discontinuation from the study, we will follow the subject until the event is resolved or until the subject is discharged to alternate care.

11.5. Study Stopping Rules

The study may be prematurely terminated for the following reasons:

The Study PI or ISM may terminate this study at any time. Reasons for termination may include, but are not limited to the incidence or severity of AEs in this study indicating a potential health hazard to subjects or unsatisfactory subject enrollment. Any serious and/or persistent noncompliance by the investigator with the protocol, the clinical research agreement, the Form FDA 1572, or other local applicable regulatory guidelines in conducting the study may also be grounds for termination of the study. The PI will promptly inform all other investigators conducting the study if the study is suspended or terminated for safety reasons and will also inform the regulatory authorities of the suspension or termination of the study and the reason(s) for the action.

Study enrollment, investigational drug, and study procedures will be suspended pending expedited review of all pertinent data by the IRB and the NIAID, if any one of the following occurs:

1. If any death occurs that is designated as related to ifetroban or to a study procedure

2. If 3 AERD enrolled trial participants experience serious non-fatal AEs related to aspirin desensitization, or if 2 AERD enrolled participants experience serious non-fatal AEs related to ifetroban/placebo, or to another study procedure.

12. Safety Monitoring and Reporting

12.1 Overview

This section defines the types of safety data that will be collected under this protocol and outlines the procedures for appropriately collecting, grading, recording, and reporting those data. Adverse events that are classified as serious according to the definition of health authorities must be reported promptly (per Section 12.5, *Reporting of Serious Adverse Events and Adverse Events*) to the sponsor DAIT/NIAID. Appropriate notifications will also be made to site principal investigators, Institutional Review Boards (IRBs), and health authorities.

Information in this section complies with *ICH Guideline E2A: Clinical Safety Data Management: Definitions and Standards for Expedited Reporting*, *ICH Guideline E-6: Guideline for Good Clinical Practice*, 21CFR Parts 312 and 320, and applies the standards set forth in the National Cancer Institute (NCI), Common Terminology Criteria for Adverse Events (CTCAE), Version 4.0: <http://ctep.cancer.gov/reporting/ctc.html>.

12.2 Definitions

12.2.1 Adverse Event (AE)

Any untoward or unfavorable medical occurrence associated with the subject's participation in the research, whether or not considered related to the subject's participation in the research (modified from the definition of adverse events in the 1996 International Conference on Harmonization E-6 Guidelines for Good Clinical Practice) (from OHRP "Guidance on Reviewing and Reporting Unanticipated Problems Involving Risks to Subjects or Others and Adverse Events (1/15/07)" <http://www.hhs.gov/ohrp/policy/advevntguid.html#Q2>)

For this study, an adverse event will include any untoward or unfavorable medical occurrence associated with:

- **Study therapy regimen:**
 - Ifetroban: any AEs occurring during the treatment period after randomization and for 14 days after completion or discontinuation from the study.
 - Aspirin desensitization: any AEs occurring during the aspirin desensitization and for 14 days after completion or discontinuation from the study.
 - The aspirin challenge/desensitization procedures are expected to produce a set of aspirin-induced reaction symptoms, which can vary from patient-to-patient, and are listed in **Section 5.4 Risks of aspirin desensitization procedure**. These common and transient aspirin-induced reaction symptoms will not be reported as AEs. However, if any of the following events occur that are associated with the aspirin-induced reaction during the desensitization, they WILL be reported as AEs:
 1. Aspirin-induced bronchoconstriction with a fall in FEV1 of >50% from that morning's baseline value.
 2. Aspirin-induced symptomatic hypotension (fall in SBP of 20% or more from that morning's baseline value).

3. Any aspirin-induced reaction that produces symptoms severe enough to warrant the use of injectable epinephrine (including, but not limited to, angioedema of the respiratory tract and prolonged hypotension), as deemed medically necessary by the treating study physician.
4. Any aspirin-induced reaction that produces symptoms severe enough to warrant transfer of the patient to the Emergency Department for monitoring, as deemed medically necessary by the treating study physician.

- **Study mandated procedures:** Blood draw: Any AE occurring 24 hours after blood collection. Nasal sample collection: Any AE occurring 24 hours after procedure.

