3.2. Primary Outcome

The primary outcome is the calculated dose of aspirin that induces an increase in the Total Nasal Symptom Score (TNSS) of 2 from the baseline value, or “PD₂”.

The PD₂ will be calculated during the aspirin desensitization at Visit 2 as follows:

$$inverselog_{10} \left(\frac{(2 - (PrevTNSS - BaselineTNSS)) \times (\log_{10} ProvocDose - \log_{10} PrevDose)}{(MaxTNSS - BaselineTNSS) - (PrevTNSS - BaselineTNSS)} + (\log_{10} PrevDose) \right)$$

Where:

Baseline TNSS = TNSS score prior to administration of aspirin

PrevTNSS = TNSS score immediately previous to onset of aspirin reaction

MaxTNSS = Maximum TNSS score recorded during 3-hour observation period during aspirin reaction

ProvocDose = Dose of aspirin that provoked a reaction

PrevDose = Dose of aspirin that preceded the provocative dose

We have used this outcome in our current nearly completed study of 40 patients with AERD and have found that it is an accurate reflection of reaction severity and aspirin sensitivity. As PD₂ is based both on the provocative dose of aspirin that induced a reaction and on the severity of the reaction, it reflects each patient’s sensitivity to aspirin. Nasal and upper respiratory symptoms (congestion, rhinorrhea, sneezing, nasal and ocular itching) in response to the provocative dose of aspirin will be monitored based on a 0- to 5-point scale (0, none; 1, little; 2, moderate; 3, quite a bit; 4, severe; 5, very severe) as described.³¹ The maximum TNSS possible (indicating maximal symptoms) is 40.

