Ifetroban was the subject of 24 controlled and uncontrolled human pharmacology and pharmacokinetic studies. It was also the subject of eight placebo-controlled clinical trials for various cardiovascular indications which are summarized in **Table 2**. The incidence rate of adverse events was generally comparable between the ifetroban-treated subjects and the placebo-treated subjects. Bradycardia was reported more often in the ifetroban group (N=32; 3.3%) than with placebo (N=7; 1.2%). Gastrointestinal events tended to occur more often in the ifetroban subjects than in the placebo subjects, although incidence rates were too small to suggest a trend or pattern. The most frequently reported adverse events (N; % ifetroban vs. N; % placebo) were headache (N=80; 8.4 vs. N=47; 7.7), musculoskeletal pain (N=48; 5.0 vs. N=19; 3.1), angina pectoris (N=33; 3.5 vs. N=22; 3.6), bradycardia (N=32; 3.3 vs. N=7; 1.2), myocardial infarction (N=28; 2.9 vs. N=18; 3.0), nausea/vomiting (N=25; 2.6 vs. N=10; 1.6), dyspepsia (N=24; 2.5 vs. N=9; 1.5), upper respiratory infection (N=24; 2.5 vs. N=9; 1.5), hematoma (N=23; 2.4 vs. N=8; 1.3), coronary artery bypass (N=22; 2.3 vs. N=10; 1.6), coronary angioplasty (N=21; 2.2 vs. N=10; 1.6), abdominal pain (N=20; 2.1 vs. N=10; 1.6), and anxiety/nervousness (N=19; 2.0 vs. N=9; 1.5). All remaining events occurred at a rate less than 2.0% in both treatment groups except for dizziness which occurred in 2.1% (N=13) of placebo-treated subjects (ifetroban: N=13; 1.9%).

Table 2. Number of subjects exposed to ifetroban in clinical studies.

		Subject Exposure	
		Ifetroban	Placebo
Clinical Pharmacology/Pharmacokinetics			
	Human Pharmacology	189	49
	Pharmacokinetic	154	0
Clinical Trials			
	Silent Ischemia (CV124-008)	58	55
	Stable angina (CV124-009)	105	52
	Unstable angina (CV124-011)	315	166
	PTCA (CV124-012)	90	35
	PVD (CV124-014)	137	44
	Post MI (CV124-015)	149	149
	Forearm blood flow in HF (CV124-018)	20	23
	Venous ulcers (CV139-001)	82	83
	Total Subjects	1299	656

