5.4. Risks of Study Procedures

Risks of aspirin desensitization procedure. All individuals with AERD will experience a clinical reaction to aspirin, most often at a dose of 81 mg or below. By using the modified Scripps Institute protocol,³² limiting the study to individuals with stable asthma and no history of life-threatening reaction to COX inhibitors, and administering montelukast to all individuals undergoing the challenge, the procedure can safely be done in an ambulatory setting and is routinely performed in the Allergy Clinic at the BWH. To ensure safety of the challenge, vital signs will be obtained every 90 minutes, and patients are instructed to report any of the following symptoms; cough, dyspnea, chest tightness, rhinorrhea, congestion, sneeze, ocular pruritis and discharge. Spirometry is repeated before each dose, or at the time symptoms are reported. A decrease in pre-challenge FEV₁ of 15% or more is considered indicative of a positive lower respiratory tract reaction. In our experience, ~60% of individuals with AERD who are treated with montelukast develop airflow obstruction of this magnitude, while the remainder experience a reaction confined to the sinonasal tract. In addition to respiratory symptoms, occasionally extrapulmonary symptoms occur as well, which can include gastrointestinal manifestations (abdominal discomfort, nausea, vomiting, or diarrhea) and skin manifestations (flushing, itching, and rash). Systemic reactions that involve the cardiovascular system are very rare in this selected population.

Injectable adrenalin, oxygen, and resuscitation equipment are present in the ARC in the unlikely event of a systemic reaction, as are physicians skilled in resuscitation.

Risks of ACQ, SNOT-22, and TNSS questionnaires. There are no risks associated with questionnaires.

Risk of blood draw. Risks associated with drawing blood include some pain when the needle is inserted. There is a small risk of bruising and/or infection at the place where the needle enters the arm. Some people may experience lightheadedness, nausea or fainting. It is possible to develop an infection, but this is rare and can be treated.

Risk of spirometry. Occasionally, individuals may develop a slight dizzy feeling and/or temporary cough and/or chest discomfort when performing breathing tests. These tests are used in hundreds of laboratories throughout the world on a daily basis without harmful effects.

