2. Before aspirin is given, a urine sample will be collected for pregnancy and eicosanoid metabolites, and a nasal fluid and nasal epithelial scraping sample will be taken, along with a blood draw for CBC/differential and cellular assays.
3. Subjects will then undergo an oral aspirin desensitization procedure. They will receive an initial 40.5 mg dose of aspirin, and then every 90 minutes will be given increasing doses of 81, 162, and 325 mg aspirin.
4. Vital signs are obtained every 90 minutes during the aspirin challenge/desensitization.
5. If at any point the subject develops symptoms of a reaction, we will examine them and record the time of onset of reaction. The dose of reaction that induces an increase in TNSS of 2 or more points will be recorded as the provocative dose.
6. Following the onset of reaction, patients will be observed for a 3-hour period, during which time no more aspirin doses will be given. TNSS will be recorded at the onset of reaction and again every 30 minutes during this 3-hour period after reaction.
7. Pulmonary function testing is repeated before each dose and at the onset of reaction and if it remains within 85% of their pre-challenge FEV₁, it will be repeated every 90 minutes during the 3-hour period after reaction. If the FEV₁ falls by 15% or more from their morning pre-challenge FEV₁, they will be treated with

MDI albuterol (up to 8 puffs per administration), followed by nebulized albuterol if needed and FEV₁ will be repeated every 30 minutes until it has returned to within 85% of their morning pre-challenge FEV₁.

8. No medications (except albuterol and ipratropium) will be used for relief of symptoms during the desensitization until the 3-hour period of observation following onset of reaction is completed, unless required for a patient's safety.
9. A blood sample will be collected 1 hour after the onset of reaction for CBC/differential, platelet activation assays, and platelet-leukocyte aggregate measurements. Urine and nasal fluid samples will be collected 90 minutes after the onset of reaction, or if there is no clinical reaction at all, will be collected 90 minutes after the 325mg dose of aspirin is given.

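### Section 12.2.1 exempts transient gastrointestinal and skin symptoms on the aspirin-challenge day from AE reporting by presuming aspirin caused them, and no listed outcome records them instead

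*Combined protocol and SAP*

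**What the plan says.** Section 12.2.1 defines an adverse event without regard to relatedness. Section 12.4.3 requires recording whatever the relationship, and Section 12.3.2 gives attribution to the site investigator first and DAIT/NIAID finally. For the challenge, Section 12.2.1 then makes an exception for the expected reaction symptoms in Section 5.4: "These common and transient aspirin-induced reaction symptoms will not be reported as AEs". Four situations override the exemption, and of these it says "they WILL be reported as AEs": an FEV1 fall above 50%, symptomatic hypotension, a reaction needing injectable epinephrine, and transfer to the Emergency Department.

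The Section 5.4 list is not confined to the airway. It adds that "occasionally extrapulmonary symptoms occur as well" and names "gastrointestinal manifestations (abdominal discomfort, nausea, vomiting, or diarrhea) and skin manifestations (flushing, itching, and rash").

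On the drug itself, Section 5.1 reports: "Gastrointestinal events tended to occur more often in the ifetroban subjects than in the placebo subjects". The same sentence cautions that the incidences were too low to indicate a trend.

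Section 3.2 describes the symptom score behind the primary outcome as "Nasal and upper respiratory symptoms (congestion, rhinorrhea, sneezing, nasal and ocular itching"). For Visit 2, Section 8.3 says: "If at any point the subject develops symptoms of a reaction, we will examine them and record the time of onset of reaction". Sections 12.8.2 and 12.8.3 base the planned safety reviews, at a minimum, on listings of reported AEs and SAEs.

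**The concern.** At Visit 2 a subject on blinded treatment who vomits after aspirin could be reacting to aspirin, to ifetroban, or to both. The exemption settles that question in advance. It labels the symptom aspirin-induced and so bypasses the attribution step that applies to every other event.

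For nasal, ocular and bronchial symptoms this costs little, because TNSS and FEV1 measure them in both arms. Gastrointestinal and skin symptoms have no such second record among the outcomes.

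The day matters. Section 7.3 prohibits NSAIDs other than the study aspirin, so Visit 2 is the first planned co-exposure in this population. A between-arm difference in tolerance, in either direction, is safety information that cannot be reliably recovered later if it was not written down.

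**Working it through.** **1. What the exemption reaches**

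| Symptom group in Section 5.4 | Exempt unless one of the four exceptions applies | Measured by a listed outcome |
|---|---|---|
| Nasal, ocular | Yes | TNSS |
| Lower airway | Yes | FEV1 |
| Gastrointestinal | Yes | None |
| Skin | Yes | None |

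The outcomes in Sections 3.2 to 3.4 are PD2 (from TNSS), FEV1, ACQ, SNOT-22, FeNO, mediator levels and cell assays. One limit on this reading: Section 3.2 names five TNSS symptoms scored 0 to 5, which gives 5 × 5 = 25, but states a maximum of 40, which implies 40/5 = 8 items. The other three are not named. I assume they too are nasal or upper respiratory, as the section describes the score. The symptoms that Section 5.4 tells patients to report during the challenge are also respiratory, nasal and ocular only.

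Section 12.3.1 records events of grade 2 or higher, so grade 1 symptoms would go unrecorded with or without the exemption. The loss due to this rule is essentially transient grade 2 events that trigger none of the four exceptions.

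**2. The earlier ifetroban data**

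Inputs: the event counts in Section 5.1 and the clinical-trial rows of Table 2.

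Ifetroban: 58 + 105 + 315 + 90 + 137 + 149 + 20 + 82 = 956. Placebo: 55 + 52 + 166 + 35 + 44 + 149 + 23 + 83 = 607.

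Risk ratio RR = (a/956)/(b/607). The 95% interval is exp(ln RR ± 1.96 × SE), with SE = √(1/a − 1/956 + 1/b − 1/607). For nausea/vomiting, SE = √(1/25 − 1/956 + 1/10 − 1/607) = 0.371.

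| Term | Ifetroban | Placebo | Stated % | Recomputed % | RR (95% CI) | Fisher p |
|---|---|---|---|---|---|---|
| Nausea/vomiting | 25 | 10 | 2.6 vs 1.6 | 2.62 vs 1.65 | 1.59 (0.77 to 3.28) | 0.23 |
| Dyspepsia | 24 | 9 | 2.5 vs 1.5 | 2.51 vs 1.48 | 1.69 (0.79 to 3.62) | 0.21 |
| Abdominal pain | 20 | 10 | 2.1 vs 1.6 | 2.09 vs 1.65 | 1.27 (0.60 to 2.69) | 0.58 |
| Sum of the three | 69 | 29 | not stated | 7.22 vs 4.78 | 1.51 (0.99 to 2.30) | 0.054 |

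The stated percentages reproduce to within rounding. The direction is the same for all three terms, but every interval includes 1. The summed row may count a subject more than once. Section 5.1 reports no excess of flushing, itching or rash.

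**3. What 20 per arm could show**

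At the earlier nausea/vomiting rates alone, the expected counts are 20 × 0.026 = 0.52 and 20 × 0.016 = 0.32. The chance of at least one event is 1 − 0.974^20 = 41% on ifetroban and 1 − 0.984^20 = 28% on placebo. Those rates come from whole trials in other patients, not from one challenge day.

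The documents give no rate for gastrointestinal symptoms caused by the challenge. Assuming a placebo-arm rate of 5% to 30%, the power of a two-sided Fisher test at 0.05 with 20 vs 20 is:

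| Assumed placebo rate | RR 1.6 | RR 2 | RR 3 |
|---|---|---|---|
| 5% | 1% | 2% | 7% |
| 10% | 4% | 7% | 24% |
| 20% | 8% | 19% | 65% |
| 30% | 14% | 35% | 98% |

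**4. Why aspirin dose must accompany any count**

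Section 13.4.2 plans for a mean PD2 of 60 on placebo and 180 on ifetroban. PD2 is interpolated between the provocative dose and the one before it. A subject at 60 therefore reacts at the 81 mg step, having taken 40.5 + 81 = 121.5 mg. A subject at 180 reacts at the 325 mg step, having taken 40.5 + 81 + 162 + 325 = 608.5 mg. If the drug works as planned, the ifetroban arm takes more aspirin, so a raw count by arm would mix aspirin dose with drug tolerance.

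**The case against.** Exempting expected procedural reactions, with named exceptions, is a deliberate and common choice. Section 5.1 states that no significant safety concern arose when ifetroban was given with aspirin. The exemption covers only transient symptoms that are common and aspirin-induced, while Section 5.4 says the extrapulmonary ones are occasional, so a careful investigator might report them anyway. The Visit 2 examination and concomitant-medication records go to the CRF, and ondansetron or diphenhydramine use would leave a trace. The Visit 2 form is not in the documents and may already have a symptom field.

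Much of this limits the point without removing it. The cited interaction study was in healthy volunteers. The common/occasional mismatch means that two investigators could apply the rule differently. Rescue-drug use is an indirect marker, and Section 7.4 holds both drugs back until after the 3-hour observation.

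Three stronger readings are tempting and not supported:

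- **An established gastrointestinal excess on ifetroban.** The protocol's own caveat and the intervals above rule that out, and there is no skin signal at all.
- **An AE record of zero in both arms.** The epinephrine and Emergency Department exceptions, persistent or unlisted events such as gastrointestinal bleeding, and AEs during the four treatment weeks and at Phone Calls 3 and 4 all remain reportable.
- **A biased between-arm safety analysis.** Section 13.4 specifies no such test or table, so what is affected is the record itself.

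**Conclusion.** The point holds in limited form. Sections 12.2.1 and 5.4 together keep transient gastrointestinal and skin symptoms at Visit 2 out of the AE record by presuming their cause, and no listed outcome replaces that record. What is lost is essentially descriptive information on grade 2 events on the first planned day of combined exposure. With 20 per arm, a formal comparison would have 35% power at most for a doubling over the assumed 5% to 30% range, so no inferential result is at stake.

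This rests on reading the Section 5.4 list as falling within the exemption, on TNSS being confined to nasal and upper respiratory symptoms, and on there being no undisclosed symptom field on the Visit 2 form. It is worth changing because it is cheap, not because the earlier data demonstrate harm.

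**What to change.** - Reconcile Section 12.2.1, which calls the exempt symptoms common, with Section 5.4, which calls the extrapulmonary ones occasional. State plainly which symptoms are exempt, and limit the exemption to the nasal, ocular and lower-airway symptoms that TNSS and FEV1 already capture.
- Add a block to the Visit 2 form for gastrointestinal and skin symptoms: type, CTCAE grade, time, and aspirin taken so far. Complete it for every subject, including those who do not react, from the first aspirin dose until discharge. Stopping at the end of the 3-hour observation would miss the doses that follow it, and non-reactors have no such period.
- Tabulate these by arm as a separate descriptive line for reaction-phase symptoms, shown with or by aspirin dose. Provide it alongside the AE listings for the Independent Safety Monitor and DSMB, with no expedited reporting unless an event is serious.

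The cost is one CRF block and one table, filled in on a day when staff are already examining reacting subjects. More events will be recorded. Keeping them apart from the general AE listing stops them from inflating it.
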